Brief Summary	
This study is a prospective randomized trial examining the effect of tranexamic acid (TXA) and aminocaproic acid (ϵ-Ahx) with local anesthetics and thrombin in all electively created surgical wound beds in hand surgery to provide long term pain relief and decrease the use of postoperative narcotics.
 
All surgical created wounds for any hand surgery will be treated in a randomized fashion with the following four arms:
 
1. Bupivacaine + lidocaine2. Bupivacaine + lidocaine + thrombin3. Bupivacaine + lidocaine + thrombin + tranexamic acid4. Bupivacaine + lidocaine + thrombin + aminocaproic acid 
All are applied topically to surgical bed prior to closure of skin.

Phase	N/A
Objectives	
The primary objective of this study is to evaluate the effectiveness of topical antifibrinolytics, thrombin and local anesthetics on postoperative pain control in patients undergoing elective hand surgery. We want to determine the efficacy of this treatment over treatment with thrombin and local anesthetics and just local anesthetics alone to the same population of patients.
 
The secondary objective of the study is to reduce the amount of opioid pain medications required postoperatively for routine hand surgery procedures.

Methodology	Prospective single blinded study
Endpoint	Degree of pain and amount of adjuvant pain medication used at 1 month post surgery
Study Duration	12 months
Participant Duration	Pre-operative visit occurs up to 3 months prior to surgery Final Study visit occurs up to 6 weeks after surgery. Primary endpoint (returning completed pain diary to study staff) occurs at Day 14. Participants remain enrolled in the study up until their standard of care post-op visit, which typically occurs 4-6 weeks after surgery. Participation is complete when participants complete their final standard of care post-op visit.
Duration of IP administration	Applied topically to surgical bed prior to closure of skin
Population	Nontraumatic, elective upper extremity (hand) surgery cases, age 18 or older
Study Sites	NYU Langone Health Bellevue Hospital Center
Number of participants	40 (10 per study arm)
Description of Study Agent/Procedure	Applied topically to surgical bed prior to closure of skin: 1. Bupivacaine + lidocaine (reference therapy) 2. Bupivacaine + lidocaine + thrombin 3. Bupivacaine + lidocaine + thrombin + tranexamic acid 4. Bupivacaine + lidocaine + thrombin + aminocaproic acid
Reference Therapy	All study agents have been used as standard of care

CONFIDENTIAL

This material is the property of the NYU School of Medicine and Langone Medical Center. Do not disclose or use except as authorized in writing by the study sponsor
Interventional Template Version: 11 January 2019

Statistical Analysis	To evaluate PACU time as a function of each group, a one way analysis of variance test followed by a Tukey-Kramer post hoc test will be performed. To assess the number of pain pills need as a function of each group, a Kruskal-Wallis test followed by a Dunn post hoc analysis will be performed.
----------------------	---

Schematic of Study Design

Screening/Baseline Visit (up to 3 months prior to day of surgery)

1. Obtain informed consent of potential participant verified by signature on written informed consent for screening form.
2. Review medical history to determine eligibility based on inclusion/exclusion criteria.
3. Review medications history to determine eligibility based on inclusion/exclusion criteria.
4. Perform medical examinations needed to determine eligibility based on inclusion/exclusion criteria.
5. Schedule day of surgery where primary intervention will be performed.
6. Provide participants with information regarding tranexamic acid, and operative steps for administration of drugs into surgical wound prior to closure.
7. Provide participants with log books.
8. Randomize patient using sealed envelope method.

Day of Surgery

1. Verify patient still meets inclusion/exclusion criteria.
2. Administer study treatment
3. Patient fills out Day 1 of pain diary

Intermediate Visits

1. Participants will be called via phone each day by the study team to ensure they have completed their daily log of numerical pain rating scale and number of pain pills taken.
2. They will arrive for an intermediate visit on their first postoperative visit (variable time, between 3-14 days postoperatively). Log books will be collected only after postoperative day 14.

Final Study Visit (up to 6 weeks post surgery)

Pain logs will be collected from participants who have not already returned them to study staff. The participants will be released of their duties to the study once the log books have been returned to the physicians. They will continue their routine follow up per the follow up schedule for each hand surgery procedure. No additional data is collected for study purposes at post-op visits beyond data collected per standard of care.

CONFIDENTIAL

2.1 Background Information and Relevant Literature

Opioid pain medication use and its abuse has been an epidemic in the United States for greater than the past decade. It has been shown that for the past decade and greater, the prescribing patterns for opioid pain medications have drastically changed; however, are still relatively high compared to 1999.⁶ It has been also shown that many physicians prescribe an excessive amount of opioids to patients undergoing elective upper extremity surgeries.

This study aims to potentially minimize the use of opioid pain medication following outpatient elective hand surgery procedures. The PI of this current project has already published an article that shows the superior pain control postoperatively utilizing topical thrombin and local anesthetic. Even so, there is limited study for the use of intraoperative techniques to control post operative pain.

2.2 Name and Description of the Investigational Agent

1. Topical lidocaine and bupivacaine alone; in this treatment group, each solution will include 5 ml of 1% lidocaine, 5 ml of 0.25% bupivacaine
2. Topical lidocaine and bupivacaine with thrombin; in this treatment group, each solution will include 5 ml of 1% lidocaine, 5 ml of 0.25% bupivacaine, 10000 units of thrombin
3. Topical lidocaine and bupivacaine with thrombin and tranexamic acid; in this treatment group, each solution will include 5 ml of 1% lidocaine, 5 ml of 0.25% bupivacaine, 10000 units of thrombin, and 500 mg of tranexamic acid
4. Topical lidocaine and bupivacaine with thrombin and aminocaproic acid; in this treatment group, each solution will include 5 ml of 1% lidocaine, 5 ml of 0.25% bupivacaine, 10000 units of thrombin, and 1000 mg of aminocaproic acid

Tranexamic acid:

CONFIDENTIAL

This material is the property of the NYU School of Medicine and Langone Medical Center. Do not disclose or use except as authorized in writing by the study sponsor
Interventional Template Version: 11 January 2019

FDA-approved usage for intravenous tranexamic acid (TXA) is for heavy menstrual bleeding and short-term prevention in patients with hemophilia.

We plan on using a total dose of 500 mg (20 mL) total for each case.

Aminocaproic acid:

FDA notes that aminocaproic acid is useful in enhancing hemostasis when fibrinolysis contributes to bleeding. Aminocaproic acid inhibits both the action of plasminogen activators and to a lesser degree, plasmin activity. The fibrinolysis-inhibitory effects of aminocaproic acid appear to be exerted principally via inhibition of plasminogen activators and to a lesser degree through antiplasmin activity. Parenteral drug products should be inspected visually for particulate matter and discoloration prior to administration, whenever solution and container permit.

We will use a total of 1000 mg total for each case.

Recombinant Human Thrombin:

Topical thrombin is approved by the FDA as an aid to hemostasis whenever oozing blood and minor bleeding from capillaries and small venules is accessible and control of bleeding by standard surgical techniques is not sufficient.

Recombinant human thrombin is available as 5000-unit and 20,000-unit vials of sterile recombinant topical thrombin lyophilized powder for solution. When reconstituted as directed, the final solution contains 1000 units/mL.

For our topical application, we will use a total of 10000 units per open surgical study arm involving use of Thrombin.

Lidocaine Hydrochloride with Epinephrine:

Topical lidocaine product is approved for FDA as an amide local anesthetic in any indication for relief of pain associated with superficial minor surgery and as an adjunct for local infiltration anesthesia. It is frequently used as a standard local anesthetic for surgical procedures.

Each mL contains lidocaine hydrochloride and epinephrine, with 0.5 mg sodium metabisulfite as an antioxidant and 0.2 mg citric acid as a stabilizer.

We plan on using a total of 5 mLs per open surgical study arm involving lidocaine hydrochloride and epinephrine.

Bupivacaine Hydrochloride with Epinephrine:

Topical bupivacaine is approved for FDA as indicated for the production of local anesthesia for procedures by infiltration injection. It is frequently used as a standard local anesthetic for surgical procedures.

Each mL contains bupivacaine hydrochloride and 0.005 mg epinephrine, with 0.5 mg sodium metabisulfite as an antioxidant and 0.2 mg citric acid (anhydrous) as stabilizer.

We plan on using a total of 5 mLs per open surgical study arm involving Bupivacaine Hydrochloride with Epinephrine.

The clinical investigation of the drugs noted above is exempt from IND requirements in accordance with 21 CFR 312.2(b) because:

(i) The investigation is not intended to be reported to FDA as a well-controlled study in support of a new indication for use nor intended to be used to support any other significant change in the labeling for the drug;

CONFIDENTIAL

This material is the property of the NYU School of Medicine and Langone Medical Center. Do not disclose or use except as authorized in writing by the study sponsor
Interventional Template Version: 11 January 2019

(ii) If the drug that is undergoing investigation is lawfully marketed as a prescription drug product, the investigation is not intended to support a significant change in the advertising for the product;

(iii) **As noted in section 2.2.2., the investigation does not involve a route of administration or dosage level or use in a patient population or other factor that significantly increases the risks (or decreases the acceptability of the risks) associated with the use of the drug product;**

(iv) The investigation is conducted in compliance with the requirements for institutional review set forth in part 56 and with the requirements for informed consent set forth in part 50; and

The investigation is conducted in compliance with the requirements of 312.7.

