2.2.1 Clinical Data to Date

Tranexamic acid is a synthetic derivative of the amino acid lysine. Its mechanism of action is via inhibition of fibrinolysis by blocking the lysine binding site on plasminogen. It acts as a competitive inhibitor of conversion of plasminogen to plasmin and at higher concentrations a non-competitive inhibitor of plasmin.

Thrombin is a serine protease coagulant that both converts soluble fibrinogen into insoluble fibrin strands and activates factor XIII to catalyze covalent crosslinking of these strands, thereby forming a stable fibrin clot. It also promotes platelet aggregation at the site of vascular injury, via the activation of specific protease-activated receptors. Thus, exogenous topical thrombin directly activates the terminal stages of blood clot formation at the site of application.

Bupivacaine is an amino-amide local anesthetic. Onset of action is 1-17 min. Duration of action (route and dose-dependent) 2-9 hr. Half life: neonates 8.1 hours, adults: 2.7 hours. Time to peak plasma concentration (for peripheral, epidural, or caudal block): 30-45 min. Protein binding: about 95%. Metabolism: hepatic. Excretion: renal (6% unchanged).

Lidocaine is an amino-amide local anesthetic. Onset of action is 2-4 min. Duration of action (route and dose-dependent) 2 - 3.5 hr. Half life: 1.5-2 hr. Protein binding: 60-80%. Metabolism: hepatic. Excretion: renal.

Previous work by our group showed that the addition of topical thrombin to local anesthetic at the end of elective hand surgery provides for sustained postoperative pain control. Patients in that study who received thrombin and local anesthetic before wound closure had lower pain levels and were discharged from the PACU sooner than those who received local anesthetic alone. We hypothesize that the addition of a topical antifibrinolytic agent such as tranexamic acid with thrombin and local anesthetic at the end of elective hand surgery will provide even greater pain relief through the formation of a stable clot that prolongs the effect of local anesthesia. We hypothesize we will see even lower pain scores and lower number of pain pills and shorter PACU times in the postoperative period in the groups with a tranexamic acid + thrombin + local anesthetic than the groups with just thrombin + local anesthetic.

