2.2.2 Dose Rationale (if applicable)

The dosages that we use for treatment groups 1 and 2 in this research study are consistent with the dosages given per standard of care at this institution. Treatment groups 1 and 2 are considered equivalent and are both used in our practice as standard of care.

Previous literature has shown that topical application of tranexamic acid and aminocaproic acid decreases postsurgical bleeding after major surgical procedures, and that this is a promising strategy to improve surgical outcomes (Ipema H et al., Use of topical tranexamic acid or aminocaproic acid to prevent bleeding after major surgical procedures). Clinical trials, case reports, and meta-analyses describing topical use of tranexamic acid or aminocaproic acid to prevent postoperative bleeding all

CONFIDENTIAL

This material is the property of the NYU School of Medicine and Langone Medical Center. Do not disclose or use except as authorized in writing by the study sponsor
Interventional Template Version: 11 January 2019

showed reduction of postoperative blood loss. The dosages used in these studies are as follows: 4 trials used solutions containing tranexamic acid (1-2.5 g in 100-250 mL of 0.9% NaCl), and 1 trial assessed a solution containing aminocaproic acid (24 g in 250 mL of 0.9% NaCl).

Literature has shown that topical TXA is safe and effective for reducing perioperative blood loss. It is therefore a great agent for controlling perioperative blood loss and potentially lowers transfusion rates and shortens length of hospital stay (Wei W et al., Comparison of intravenous and topical tranexamic acid in total knee arthroplasty). Off-label use of topical TXA in surgery has demonstrated that patients who received topical TXA were associated with a shorter length of hospital stay (Teoh T et al., Prophylactic Topical Tranexamic Acid Versus Placebo in Surgical Patients A Systematic Review and Meta-Analysis*).

Tranexemic acid: We plan on using a total dose of 500 mg (20 mL) total for each case.

Aminocaproic acid: We will use a total of 1000 mg total for each case.

Recombinant Human Thrombin: For our topical application, we will use a total of 10000 units per open surgical study arm involving use of Thrombin.

Lidocaine Hydrochloride with Epinephrine: We plan on using a total of 5 mLs per open surgical study arm involving lidocaine hydrochloride and epinephrine.

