Bupivacaine Hydrochloride with Epinephrine: We plan on using a total of 5 mLs per open surgical study arm involving bupivacaine hydrochloride with epinephrine.

Each study arm will receive an intraoperative local block at the site of surgery by the operative surgeon prior to incision, in accordance with our institutional standard of care..

2.3 **Rationale**

Pain management immediately post operatively is often difficult without utilizing opioids. With increasing concern about opioid addiction, our study hopes to elucidate other methods of immediate post operative pain control that will limit the amount of opioids taken after having elective hand surgery.

We propose that the utilization of thrombin, topical anesthetic, and an antifibrinolytic will improve post operative pain control.

2.4 **Potential Risks & Benefits**

2.4.1 **Known Potential Risks**

Lidocaine: Tinnitus, cardiac irritability, and neurological disturbance have been noted only when patients receive more than 4mg/kg of lidocaine. In this study, we are using less than 1mg/kg, which is a lot lower than the maximum amount of medication given to patients.

Bupivacaine: Tinnitus, headache, difficulty with urination, chest discomfort, problems with speech, cardiac irritability, and neurological disturbance have been noted only when patients receive more than 3mg/kg of bupivacaine. In this study, we are using less than 1mg/kg, which is a lot lower than the maximum amount of medication given to patients.

It is well known that bupivacaine can cause adverse effects (cardiotoxicity, and central nervous system toxicity); however, the dose and route of administration in our study minimizes these risks, as noted above.

Thrombin: Major risks of thrombin have only been seen in systemic usage. We are using thrombin only topically, in order to minimize side effects that may occur when used systemically. Topical thrombin per

CONFIDENTIAL

the FDA has risks of anaphylactic reactions that may occur in the clinical trial with similar frequency in the two study groups. The most common adverse event reported was procedural complications and pruritus. This risk is seen in patients with amide anesthetic sensitivity and we will screen patients for this preoperative and exclude patients with this potential risk.

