6.1.2 Dosing and Administration

Tranexemic acid:

We plan on using a total dose of 500 mg (20 mL) total for each case.

Aminocaproic acid: We will use a total of 1000 mg total for each case.

Recombinant Human Thrombin:

For our topical application, we will use a total of 10000 units per open surgical study arm involving use of Thrombin.

Lidocaine Hydrochloride with Epinephrine:

We plan on using a total of 5 mLs per open surgical study arm involving lidocaine hydrochloride and epinephrine.

Bupivacaine Hydrochloride with Epinephrine:

We plan on using a total of 5 mLs per open surgical study arm involving bupivacaine hydrochloride with epinephrine.

Each study arm will receive an intraoperative local block at the site of surgery by the operative surgeon prior to incision.

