- The patients will be counseled on the study objectives and methods of data collection. The numerical pain rating scale will be explained in detail to the patient.
- The patients will be administered a pain diary in which they will be able to log their daily pain level at the same time each day (AM) based on the numeric pain scale (1-10). They will also be instructed to log their pain medication usage and the number of pills of Norco 5/325 mg that are consumed. This log will continue daily for a total of 14 days postoperatively.

The first visit will be the initial evaluation of the patient when they present for their individual hand surgery evaluation. If they qualify for their study, an initial preoperative pain scale will be used to assess their pain level.

The next assessment will be on the day of surgery. The patient will be evaluated in the preoperative holding area and another pain level evaluation will be done for a POD#0 timepoint.

The patient will be evaluated in PACU for total time in PACU.

Each patient will receive their log book and take it home with them. The patients will be called on each day by the study team to ensure that they have been logging their daily pain score. The study team will call the patient for this purpose.

The patients will be seen in person on their first postoperative visit (approximately 1-2 weeks later). If this is prior to postoperative day 14, they will follow up again in hand clinic after day 14 (in 4-6 weeks post-surgery) to submit their log books.

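### Tranexamic acid appears to come with 20 mL of fluid that arm 2 does not get, so the test of adding it is mixed with a volume and concentration difference

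*Combined protocol and SAP*

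**What the plan says.** Section 2.2 lists four mixtures. Arms 2 and 3 share 5 mL of 1% lidocaine, 5 mL of 0.25% bupivacaine and 10000 units of thrombin, and arm 3 adds TXA: "each solution will include 5 ml of 1% lidocaine, 5 ml of 0.25% bupivacaine, 10000 units of thrombin, and 500 mg of tranexamic acid".

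The TXA volume comes from a separate sentence that appears in Sections 2.2, 2.2.2 and 6.1.2: "We plan on using a total dose of 500 mg (20 mL) total for each case". The only thrombin strength given is in Section 2.2: "When reconstituted as directed, the final solution contains 1000 units/mL". Aminocaproic acid in arm 4 is given as 1000 mg with no volume.

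No section states a final volume for any arm, names the thrombin diluent used in the trial, or adds saline or another vehicle to arm 2. Sections 4.1 and 10.1.1 nevertheless call the trial placebo-controlled.

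Section 2.2.1 states the TXA hypothesis as lower pain scores, fewer pills and shorter PACU times "in the groups with a tranexamic acid + thrombin + local anesthetic than the groups with just thrombin + local anesthetic". Section 3.1 makes superiority over the thrombin-plus-anesthetic arm part of the primary objective.

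**The concern.** The arm 3 versus arm 2 contrast is meant to isolate TXA. If TXA arrives in 20 mL of fluid and arm 2 receives nothing in its place, the two arms also differ in how much fluid enters the wound and in how concentrated the anesthetic and thrombin are.

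The proposed mechanism in Section 2.2.1 is a stable clot that makes the local anesthetic last longer. Anesthetic and thrombin are the working parts of that mechanism, and both would be more dilute in only one of these two arms. Because the difference goes with the arm, randomization does not balance it and no covariate can adjust for it. A positive or a null result would be open to two explanations.

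**Working it through.** The plan gives no volume per arm, so there is no stated figure to reproduce. The check adds up the stated components.

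**Inputs** (Sections 2.2 and 6.1.2)
- Lidocaine: 5 mL × 10 mg/mL = 50 mg in both arms.
- Bupivacaine: 5 mL × 2.5 mg/mL = 12.5 mg in both arms.
- Thrombin: 10000 units in both arms; at 1000 units/mL, 10000 / 1000 = 10 mL.
- TXA: 500 mg in 20 mL, arm 3 only.

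**Formulas.** Volume = sum of component volumes. Concentration = dose / volume.

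**Most natural reading** (thrombin as reconstituted, TXA added as 20 mL, whole mix applied)
- Arm 2: 5 + 5 + 10 = 20 mL.
- Arm 3: 5 + 5 + 10 + 20 = 40 mL.

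| | Arm 2 | Arm 3 |
|---|---|---|
| Lidocaine, mg/mL | 50/20 = 2.5 | 50/40 = 1.25 |
| Bupivacaine, mg/mL | 12.5/20 = 0.625 | 12.5/40 = 0.3125 |
| Thrombin, units/mL | 10000/20 = 500 | 10000/40 = 250 |

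Each concentration in arm 3 is half that in arm 2.

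**Other readings.** The mixing steps below are assumptions, because the protocol does not describe them.

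| Reading | Arm 2, mL | Arm 3, mL | Volume ratio |
|---|---|---|---|
| Thrombin powder dissolved in the anesthetic, 20 mL TXA added | 10 | 30 | 3 |
| Thrombin reconstituted in arm 2, TXA solution used as its diluent in arm 3 | 20 | 30 | 1.5 |
| 20 mL is the final arm 3 mix, thrombin takes 10 mL in arm 2 | 20 | 20 | 1 |
| 20 mL is the final arm 3 mix, thrombin powder dissolved in the anesthetic in arm 2 | 10 | 20 | 2 |

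The final-mix reading fits the text less well. The sentence ties 20 mL to the TXA dose, and if thrombin takes 10 mL, then 20 − 10 − 10 = 0 mL is left for TXA.

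The ratio therefore runs from 1 to 3, with 2 on the most natural reading. Total prepared doses of lidocaine, bupivacaine and thrombin are equal in every row.

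**The case against.** **The volumes are inferred.** The 1000 units/mL sentence describes the product beside its vial sizes; the trial's own thrombin instruction is in units only. The arm list gives TXA in mg only. This objection stands: 20 versus 40 mL is a reading of the text and not a stated figure, and one reading gives no difference. It does not remove the point, because equality needs the less natural meaning of 20 mL together with a particular thrombin preparation, and the protocol states neither.

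**No effect on results is shown.** This also stands. The documents hold no data on wound retention or concentration-response, and "Each study arm will receive an intraoperative local block at the site of surgery by the operative surgeon prior to incision". The stated durations in Section 2.2.1 are 2-3.5 h for lidocaine and 2-9 h for bupivacaine, while home pain scores are logged each morning to day 14. Later scores would be touched only if clot does prolong the anesthetic, which is what the trial hypothesizes.

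**Dilution could only hide a TXA benefit.** A reader might infer that arm 3 is underdosed and the comparison biased against TXA. The documents do not support that. The prepared doses are equal, and nothing in the text shows whether a larger, weaker volume acts worse, better or the same.

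**Unmatched volumes may be deliberate.** Section 2.2.2 says "Treatment groups 1 and 2 are considered equivalent and are both used in our practice as standard of care", and comparing regimens as used in practice is a legitimate aim. Adding saline moves arm 2 away from that practice. This is a real cost and a reason to keep the added volume small. But the hypothesis in Section 2.2.1 concerns what TXA adds, and a contrast that also changes the volume answers that less cleanly.

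**Conclusion.** The point holds as a design weakness worth correcting. On the most natural reading, arm 3 has twice the volume of arm 2 and half the concentration of lidocaine, bupivacaine and thrombin. That rests on three assumptions: thrombin reconstituted to 1000 units/mL, 20 mL as the volume of the TXA component, and the whole mix applied. Across the other readings the ratio is 1 to 3.

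It goes beyond missing detail, because the 20 mL is stated and, taken as the component volume, creates a difference tied to arm that analysis cannot remove. Whether it changes pain, pill counts or PACU time cannot be determined from the documents. The outcomes most plausibly exposed are PACU time, a secondary endpoint, and the earliest postoperative pain scores.

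**What to change.** In Sections 2.2 and 6.1.2, set one common final volume for arms 2 to 4:
- Give the 500 mg of TXA in the smallest volume the pharmacies can supply, for example 5-10 mL.
- Give the 1000 mg of aminocaproic acid in arm 4 in the same volume.
- Add the same volume of saline to arm 2.
- State the thrombin diluent and volume.
- If 20 mL is not the volume of the TXA component, correct it in Sections 2.2, 2.2.2 and 6.1.2.

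With thrombin at 10 mL, the common volume is 20 + 5 = 25 mL or 20 + 10 = 30 mL.

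**Cost.** One preparation instruction and a little saline; no extra patients or visits. Arm 2 concentrations fall from the standard-of-care solution by 1 − 20/25 = 20% with 5 mL, or 1 − 20/30 = 33% with 10 mL.

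**To check.** The stock strengths needed are 500/10 = 50 to 500/5 = 100 mg/mL for TXA, and 1000/10 = 100 to 1000/5 = 200 mg/mL for aminocaproic acid. The documents do not say what the two sites hold.

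Arm 1 can stay as standard of care. Its smaller volume (5 + 5 = 10 mL) should be noted as a limit when it is compared with the other arms.
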